### **3.1 Sample Size Considerations**

For each cohort in Part 1 of the study a sample size of 6 patients will provide 83% power to detect a 3 mm Hg within group change from pre-dose assuming a standard deviation of 2 and two-sided alpha = 0.05, based on a one-sample t-test. With larger standard deviations ( $\geq$ 2.5) the power to detect this difference is  $<$ 66%.

For Part 2, the sample size will provide  $>$ 90% power to detect within-group mean change from baseline of at least a 3 mm Hg for the primary endpoint assuming a standard deviation of 2.5 with two-sided alpha = 0.05. In addition, power calculations were performed for the comparison of each dose of AGN-227535 versus Timolol. These calculations consider treatment differences (AGN-227535 minus Timolol) mean changes from baseline in study eye IOP in the mITT population at Day 14/Exit.

The power to detect treatment group differences from -1 to -4 mm Hg with common standard deviations (SDs) ranging from 2.5 to 3.5, based on a two-sample t-test are shown in the Table below.

**Power Calculations for Study Part 2 Tests of Treatment Difference***(AGN-227535 N = 24; Timolol N = 12; alpha = 0.05)*

Treatment Group Difference	Common SD	Power (%)
-4	2.5	99
	3	96
	3.5	88
-3	2.5	91
	3	78
	3.5	65
-2	2.5	59
	3	45
	3.5	35
-1	≥2.0	≤20

Additional sample size calculations were performed for tests of non-inferiority of either dose of AGN-227535 to Timolol. These calculations considered a non-inferiority margin of 1.5 mm Hg and one-sided  $\alpha = 0.025$ . With a treatment group difference of -1 mm Hg, the power ranged from 50% for a common SD of 3.5 to 78% for a common SD of 2.5.

The calculation was based on the non-inferiority tests for the difference between two means using t-test as implemented in the commercial software PASS version 16.0.3 (2018).

### 3.2 Randomization and Study Eye Assignment

Part 1: No randomization is involved because all subjects in the same cohort receive the same treatment. If only one eye qualifies, the study medication will be administered to that eye. If both eyes qualify, the eye with the higher IOP at Baseline (Day -1) Hour 0 will be the study eye and will receive study medication. If both eyes have the same IOP value at this timepoint, the right eye will be the study eye.

Part 2: Subjects will be randomly assigned to 1 of up to 3 treatment arms (based on results from Part 1) in a 2(2):1 allocation ratio to receive 1 of up to 2 AGN-227535 concentrations or timolol. To ensure balance of elements that could influence the IOP-lowering effects across treatment groups, the randomization will be stratified by baseline (Hour 0) IOP ( $\leq 25$  mm Hg;  $> 25$  mm Hg). The randomization scheme will be prepared by Whitecap Biosciences or its designee. The IWRS, a module within eDC, will be used to confirm Baseline IOP eligibility and perform stratification and randomization of subjects. Subject treatment will be double-masked; neither the investigator nor the staff or subject will be aware of treatment assignment. All study treatments will be provided in similarly-appearing bottles with the same-colored bottle caps and identical cartons to maintain masking of the study. The study eye of each subject will be defined the same way as for the Part 1.

## 4 ANALYSIS POPULATIONS

Each population will be analysed based on the treatment received.

Part 1: The Safety population consisting of all treated subjects will be used for all analyses.

Part 2: The following populations will be used for analysis:

- The Safety population will consist of all treated subjects. All safety analyses will be performed using the safety population.
- The Modified Intent-to-treat (mITT) will consist of all randomized and treated subjects who provide IOP data at baseline and at least one post-baseline IOP assessment. This population will be used for analyses of efficacy data.
- The Per-Protocol (PP) population is a subset of the mITT population and consists of subjects and data points which did not have any protocol deviations deemed to have potential impact on the primary endpoint. The protocol instructs subjects to apply study treatment every morning and every evening approximately 12 hours apart each day. The 12-hour time window, if violated, may impact the Hour 0 IOP measurement on the following day. It is determined that the IOP measurement at Hour 0 on Day 4 or Day 14 visit will be excluded from the PP population if the duration between the time of evening dose on the day before and Hour 0 on the day of visit deviates from the 12-hour requirement by more than 1 hour (i.e., outside the [11 hours, 13 hours] window).

## 5 STUDY VARIABLES AND COVARIATES

### 5.1 Primary Efficacy Endpoints (Part 2)

The primary response measure is IOP. The mean hour-matching IOP change from baseline will be the primary efficacy endpoint. Also see section 1.1.

### 5.2 Secondary and Other Efficacy Endpoints (Part 2)

IOP values at each scheduled hour of Day 14/Exit. The mean IOP value will be the secondary efficacy endpoint. Also see section 1.1.

### 5.3 Subgroup Analyses (Part 2)

Subgroup analysis for Part 2 of the study will be performed on post hoc basis as needed, including by baseline IOP stratum, by investigational site, and by prior medication category (e.g., Timolol users vs non-users). Also, see section 1.1.

### 5.4 Safety Endpoints

All safety analyses will be performed on the Safety Population.

Safety and tolerability will be assessed by reporting of AEs, ECG, vital sign measurements, clinical laboratory results, BCVA, slit lamp biomicroscopy, macroscopic hyperemia, pupil size, visual fields, dilated fundus examination, and subject comfort.

## 6 DATA CONVENTION

Statistical programming and analyses will be performed using SAS® Version 9.4 or higher. Output will be provided in RTF and/or PDF format for tables, listings, and figures using landscape orientation. All study data will be listed by study part subject, treatment, and visit (as applicable) based on all enrolled or safety subjects. Subject data listings will be organized by study part, cohort treatment groups.

One database lock will occur when all subjects (both Part 1 and Part 2) have either completed the study or discontinued from the study prematurely, and all data queries have been resolved. Randomization release will occur following the database lock.

Change from baseline for all variables will be hour-matched. When there is no hour matched value (for example, cup-to-disc ratio), change from baseline will be calculated from post baseline values minus the baseline.

## 6.1 Missing Data

Unless otherwise stated, missing data will be handled using the following approach:

- Analyses performed for the mITT population will use the method of last observation carried forward (LOCF) to impute missing values. No imputation for missing data will be performed for the safety population.
- For start date, partial dates will have first day of the month imputed if day is missing, and January of that year will be imputed if month is missing. If both day and month are missing, January 01 will be imputed.
- For end date, partial dates will have last day of the month imputed if day is missing, and December of that year will be imputed if month is missing. If both day and month are missing, December 31 will be imputed. An exception is that missing dates of prior and concomitant medications will not be imputed.
- Where severity or relationship is missing for adverse events, most conservative imputation will be made; in that a missing severity will be imputed as 'severe' and a missing relationship as 'related'.

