### 8.2 Prior and Concomitant Medications

Prior and concomitant medications will be presented for each subject coded per the World Health Organization (WHO) Anatomical Therapeutics Chemical (ATC) Drug dictionary. Prior medication are those medications that stopped prior to dosing. Concomitant medications are those medications that either started anytime from dosing onwards or continued once subject had been dosed with study medication. Medications with partial dates that do not allow determination of whether prior or concomitant will be considered concomitant.

Prior and concomitant medications for Part 1 and 2 of the study will be listed separately. This listing will be presented for ocular and non-ocular prior and concomitant medications.

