### **10.1 Safety Endpoint Analysis**

#### **10.1.1 Adverse Events**

All adverse events (AEs) reported during the study will be recorded and coded using MedDRA version 20.1 terminology. An AE will be considered as treatment-emergent if it has an onset during the treatment period or is pre-existing and worsens after the first dose of study medication is administered. Subjects may have more than one AE per System Organ Class (SOC) and Preferred Term (PT). At each level of subject summarization, a subject will be counted once if they reported one or more events and will be reported with the highest severity. In cases where severity or relationship is missing, the most conservative approach will be taken (i.e., highest severity and assumed to be related).

For Part 2 of the study, the number, and percent of subjects with adverse events will be tabulated by PT using counts and percentages by treatment groups. This summary will include all treatment emergent adverse events (TEAEs) regardless of causality, treatment-related TEAEs, all serious AEs, treatment-related serious AEs, and all adverse events leading to premature discontinuation of study treatment. A separate summary will also be produced for TEAEs by SOC and PT. For Part 1 of the study, no summary presentation of adverse events will be carried out.

Both parts of the study will present a listing of TEAEs by SOC and PT showing adverse events location (OD, OS or non-ocular), severity, relationship, discontinuation details, and action taken. Also, listing for serious adverse events, and adverse events leading to discontinuation will be generated for both parts of the study.

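### SAP 6.1 can date an on-drug adverse event with a missing onset day before first dose, and so outside the treatment-emergent outputs (low priority)

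*SAP*

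**What the plan says.** **Start dates.** The rule in SAP 6.1 is general: "For start date, partial dates will have first day of the month imputed if day is missing". If the month is also missing, 1 January is used. The rule does not mention first dose. The one exemption is for medications: "An exception is that missing dates of prior and concomitant medications will not be imputed".

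**Treatment-emergent status.** Protocol 9.3.2 leaves the detailed TEAE definition to the SAP. Under SAP 10.1.1 an event is treatment-emergent "if it has an onset during the treatment period or is pre-existing and worsens after the first dose of study medication". That section has no rule for a partial onset date.

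**Other missing items.** SAP 6.1 takes the cautious side for two adverse-event fields: "Where severity or relationship is missing for adverse events, most conservative imputation will be made", which means severe and related. SAP 8.2 does the same for medications: "Medications with partial dates that do not allow determination of whether prior or concomitant will be considered concomitant".

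**A sentence that pulls the other way.** SAP 6.1 also says: "No imputation for missing data will be performed for the safety population". Adverse events are analysed in that population.

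**The concern.** Adverse events are collected from consent (Protocol 8.7), and screening can begin at Day -50. A real pre-treatment category therefore exists, and the onset date decides which side of first dose an event falls on. Suppose first dose is on 10 March, true onset is 14 March and the day is not recorded. The rule gives 1 March, which is before first dose, so the event is not a TEAE unless a later worsening is recorded.

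Safety is a stated objective of this first-in-human study. An event handled this way would leave the Part 2 tables of TEAEs and treatment-related TEAEs. It would also leave the TEAE listings, which cover both parts: "Both parts of the study will present a listing of TEAEs by SOC and PT". Part 1 has no adverse-event summary table, so its listings are the adverse-event output there. The SAP resolves missing severity, missing relationship and unclear medication timing towards the drug, but resolves onset date away from it.

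**Working it through.** The documents give no figure on this point, so there is none to reproduce. The shares below come from applying the two SAP rules to a simple calendar.

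**Inputs**
- Dosing period L = 14 days (SAP 3). Protocol 8.4.2 allows ±1 day, giving 13 to 15. Table 3 allows ±2 days at Day 14, giving 12 to 16. The two windows differ and need reconciling, so both are shown.
- Assumptions: first dose falls evenly on days d = 1 to 30 of a 30-day month, onset falls evenly on dosing days 1 to L, and only the day of onset is missing.

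**Count for L = 14.** There are 30 × 14 = 420 equally likely combinations.

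| Situation | Combinations | Share |
|---|---|---|
| Onset in first-dose month, d ≥ 2: dated before first dose | 315 | 75.0% |
| Onset in the next month: the 1st of that month already follows first dose | 91 | 21.7% |
| First dose on the 1st: imputed date equals first dose | 14 | 3.3% |

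**Formula.** With first dose on day d, min(L, 31 − d) onset days fall in the same month. The misdated share is (1/30) × Σ(d = 2 to 30) min(L, 31 − d)/L, which for L ≤ 29 reduces to (29.5 − L/2)/30.
- L = 12: 23.5/30 = 78.3%
- L = 13: 23/30 = 76.7%
- L = 14: 22.5/30 = 75.0%
- L = 15: 22/30 = 73.3%
- L = 16: 21.5/30 = 71.7%

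**Checks on the assumptions.** With L = 14, a 28-day month gives 287/392 = 73.2% and a 31-day month 329/434 = 75.8%. Enumerating every start date in a 365-day year gives 3850/5110 = 75.3%. For Part 1, with onset on Day 1 or 2, the same enumeration gives 694/730 = 95.1%. If the month is missing as well, 1 January precedes first dose in 5005/5110 = 97.9% of Part 2 combinations.

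**Effect on a reported rate.** In the tables, "a subject will be counted once if they reported one or more events". One misdated event therefore lowers a rate by at most 1/24 = 4.2 points in a planned AGN-227535 group or 1/12 = 8.3 points in the timolol group. It does so only if it is that subject's sole event at that level of summary.

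**Scope of the no-imputation sentence.** It cannot cover every adverse-event field, because the same list imputes severity and relationship. If it covers onset dates, a partial date is left as it stands and TEAE status is undefined. If it does not, the first-of-month rule applies. Either way the text needs settling.

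**The case against.** The strongest reply is that the case may hardly ever arise. In Part 2, adverse events are queried before first dose and on Days 4 and 14, so recall spans about 10 days at most. Part 1 ends on Day 2 with queries on site. Queries are to be resolved before database lock (SAP 6). The SAP is to be read with the CRF, and if the CRF rejects partial adverse-event dates the rule never operates. This stands, and it sets the priority. One part is weaker than it looks: Protocol 10.4.1 lists onset date among items that *should* be in the source notes, and Table 8 defines *should* as recommended rather than required.

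It can also be said that the date bullets never name adverse events and that the no-imputation sentence may exclude them. That is fair. A reader might infer that the SAP certainly classes such events as pre-treatment, but the documents support only that it can.

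Two further inferences go too far:
- That three quarters of adverse events would be lost. The 75.0% applies only to on-drug events lacking the day of onset, and their frequency is not given.
- That serious events or dose escalation would be affected. SAP 10.1.1 words its serious-event and discontinuation summaries without a treatment-emergent restriction, although Protocol 9.3.2 words the serious categories as TEAEs. Escalation and dose selection use all available data (Protocol 3.4, SAP 10.2). SAP 6 also lists all study data, so a misdated event should still appear in a listing.

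**Conclusion.** The point holds in a limited form. Where the start-date rule is applied to adverse events, an on-drug event with a missing onset day in the first-dose month is dated before first dose unless dosing began on the 1st. It is then not a TEAE unless a later worsening is recorded. This is a wrong rule rather than an omitted detail, because it runs against the SAP's own cautious handling of comparable gaps. Where the rule is not applied, TEAE status for a partial date is undefined.

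The conditional size is 75.0% for 14 dosing days, 76.7% to 73.3% for 13 to 15 days and 78.3% to 71.7% for 12 to 16 days, under the even-spread assumptions. The absolute size is unknown and probably small. Priority is low: efficacy and dose decisions are not touched, and the correction is cheap.

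**What to change.** Add to SAP 6.1:

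> For adverse events, if the known part of the start date is compatible with the month and year (or, if the month is missing, the year) of first dose in the study part in which the event was reported, or the start date is wholly missing, the first-dose date is imputed, unless the recorded (non-imputed) stop date, the date the event was first reported, or another record shows that the event began or ended before that first dose. Otherwise the first of the recorded month or year is used. If the start date is wholly missing and a record shows pre-dose onset, the event is classed as pre-treatment.

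Also state that the sentence "No imputation for missing data will be performed for the safety population" does not cover adverse-event dates, severity or relationship.

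Reasons for the details:
- The study part is named because exclusion 27 bars only prior randomization in Part 2, so a Part 1 subject can enter Part 2 and have two first doses.
- The stop date must be the recorded one. SAP 6.1 moves a partial end date to the end of the month or year, which would defeat the check.
- The report date matters because events are also queried at Screening, at Baseline and before dosing on Day 1.
- The treatment period should not be defined as ending at study exit. Protocol 8.9.1 asks that, after early exit, serious events and treatment-related non-serious events within 14 days of last dose be reported, and that definition would shut out those occurring after exit.

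**Effect.** On the same 420 combinations, events dated before first dose fall from 315 to 0, and the 91 next-month events keep their recorded month.

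**Cost.** A short SAP addition and a small change to the date derivation, with no new data. Some true pre-treatment events with a partial date and no pre-dose record will count as TEAEs. If onset is spread evenly over the W days before first dose in a 30-day month, the share falling in the first-dose month is (1/30) × Σ(d = 1 to 30) min(W, d − 1)/W. This gives 435/1500 = 29.0% for W = 50 (screening from Day -50) and 110/120 = 91.7% for W = 4 (Day -4). Both are upper bounds on the share of partially dated pre-dose events reclassified, because the record checks remove those already reported or ended before dosing.

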## 6.2 Descriptive Statistics

Descriptive statistics will be provided in 3 areas: (1) demographics and baseline characteristics for Parts 1 and 2, (2) IOP analyses as noted in Sections 5.1 and 5.2 for Part 2, and (3) adverse events analysis for Part 2.

For continuous variables, descriptive statistics will include the number of subjects (n), mean, standard deviation (SD), median, minimum and maximum. Categorical variables will be summarized using absolute and relative frequencies (i.e., counts and percentages). All data to be summarized will be presented by cohort treatment groups using appropriate descriptive statistics.

Unscheduled data, such as information from unscheduled visits or investigator comments, will be included in the data listings. In general, these data will be excluded from the summary tables unless otherwise specified.

# 7 DISPOSITION AND EXIT STATUS

## 7.1 Subject Disposition

Subject disposition (completed, discontinued and reason for discontinuation) for Part 1 of the study will be listed for all treated subjects by cohort treatment groups. For Part 2 of the study, subject disposition will be listed for all randomized subjects by cohort treatment groups.

## 7.2 Extent of Study Drug Exposure

Exposure to treatment group for Part 1 of the study will be listed for all treated subjects, and for Part 2 study, exposure to treatment group will also be listed for all randomized subjects.

For Part 2 of the study, treatment compliance will be listed by cohort treatment groups. For this, duration of exposure will be calculated as date of last dose minus date of first dose plus 1.

## 7.3 Protocol Deviations

A subject listing will be provided that includes the date of the deviation and the deviation description.

## 7.4 Screen Failures

The reason for screen failure for both Part 1 and 2 of the study will be listed.

## 8 BASELINE CHARACTERISTICS

### 8.1 Demographics and Baseline/Screening Characteristics

All demographic and baseline data for Part 1 and 2 of the study will be summarized per treatment group and overall. These will be presented for the safety population, and will include age, race, sex, ethnicity, iris color, childbearing potential for female subjects, height, and weight. A listing for demographics and baseline characteristics for Part 1 and 2 of the study will be presented showing the above parameters.

### 8.2 Prior and Concomitant Medications

Prior and concomitant medications will be presented for each subject coded per the World Health Organization (WHO) Anatomical Therapeutics Chemical (ATC) Drug dictionary. Prior medication are those medications that stopped prior to dosing. Concomitant medications are those medications that either started anytime from dosing onwards or continued once subject had been dosed with study medication. Medications with partial dates that do not allow determination of whether prior or concomitant will be considered concomitant.

Prior and concomitant medications for Part 1 and 2 of the study will be listed separately. This listing will be presented for ocular and non-ocular prior and concomitant medications.

### 8.3 Medical History

Medical history will be coded using the Medical Dictionary for Regulatory Activities (MedDRA) version 22. Subject listings of medical history will be generated separately for study part and for ocular and non-ocular data by System Organ Class (SOC) and Preferred Term (PT).

## 9 EFFICACY ANALYSIS

Part 1: Listings will be provided for all IOP measurements of the study eye and non-study eye by cohort, visit, and hour.

Part 2: Listings will be provided for all IOP measurements of the study eye and non-study eye by cohort, visit, and hour. Mean and/or median of the IOP measurements will also be presented along with hour-matched change from baseline IOP values.

Apart from listings, statistical analysis will be carried out for Part 2 of the study. Efficacy analyses are described in detail within this section. Analyses performed for the mITT population will use the method of last observation carried forward (LOCF) to impute missing values. Efficacy analyses will be presented for the study eye and non-study eye. The study eye would be considered the main analysis for each endpoint.

For Part 2, the primary efficacy analysis is the within-group mean change from baseline at hour 2, the time of peak efficacy of timolol, on Day 14. As this is an exploratory trial, all treatment comparisons will be made at the two-sided  $\alpha = 0.05$  level without adjustment for multiple comparisons.

### 9.1 Primary Efficacy Endpoint Analysis

The primary response measure is IOP. Two consecutive measurements of IOP will be taken for each eye, with the right eye measured first. If the first two measurements of either eye differ by more than two mm Hg, a third measurement will be taken for the eye. Depending on the number of measurements required and obtained, the IOP for a given eye will be represented by either the average or the median of the readings.

Baseline is defined as the value of Day -1 prior to treatment. The change from baseline for each eye at each post-baseline assessment is calculated as the IOP at that assessment minus the IOP at the corresponding hour at baseline. The primary efficacy endpoint analysis will be evaluated in the study eye.

The null hypothesis that the mean IOP hour-matching change from baseline is equal to 0 mm Hg will be tested and a corresponding 95% confidence interval will be calculated, based on the 1-sample t-test procedure at each hour on Days 4 and 14. The primary hypothesis is that at least one dose of AGN-227535 ophthalmic solution has a statistically significant within-group mean IOP change from baseline at Hour 2 on Day 14/Exit in the mITT population.

In addition, for exploratory purposes, each dose of AGN-227535 is hypothesized to be non-inferior to Timolol ophthalmic solution 0.5% with respect to change from baseline (follow-up minus baseline) in study eye IOP at each time-matched hour evaluated (hours 0, 2 4, and 8) on Day 4 and Day 14/Exit in the mITT population. The non-inferiority analyses will be performed via analysis of covariance (ANCOVA) which will have treatment as the main effect and the baseline hour-matched IOP as the covariate in the model. When there is no hour-matched baseline value (for example, 30 min post-dose), change from baseline will be calculated from baseline hour 0.

Pairwise treatment group comparisons will be performed for each individual dose of AGN- 227535 versus timolol ophthalmic solution 0.5%. A 2-sided 95% confidence interval (CI) for the treatment difference (AGN-227535 Ophthalmic Solution minus Timolol ophthalmic solution 0.5%) will be constructed based on this ANCOVA model for each AGN-227535 dose.

If AGN-227535 ophthalmic solution is determined to be non-inferior to Timolol ophthalmic solution 0.5%, further, an attempt to show superiority of AGN-227535 over Timolol will be made.

